Image Processing: After MRI and PET processing is performed, the data will be processed using the semi-automated analysis pipeline developed in CUBIT. MRI processing includes segmentation (grey, white, csf) and parcellation into different regions of interest. PET processing includes motion correction, coregistration to the MRI, determination of regional activity over time (time activity curves) and modeling of the time activity curves. The modeling requires information about the radioactivity of plasma during the scan. These techniques have been previously described. (Parsey, Ogden et al. 2010, Miller, Hesselgrave et al. 2013) Using this analysis, the metabolic rate of glucose (MRGlu) can be calculated. The arterial input function (as well as Simultaneous Estimation, for comparison) will be used to derive the regional MRGlu.

E. STATISTICS

Aim 1: Correlation between HDRS and pretreatment MRglu will be determined in the ESC and placebo treatment groups in the three specified regions. In post hoc analysis, spatial resolution will be improved through examination of correlation between whole brain voxel MRglu and HDRS using SPM8 on aligned voxel based parametric images. Our group has extensive experience performing these analyses. For both analyses, outcome possibilities include: differential treatment Δ HDRS prediction (i.e. significant correlation, with different sign for placebo and ESC; significant correlation, within different regions, for placebo and ESC; significant correlation in same region, same direction); or insignificant correlation with HDRS for both treatments. The former outcomes would be immediately clinically significant and applicable. The final option, though unlikely based on preliminary data, would also be an important finding and suggest that, either the cohort should be expanded, or additional imaging/clinical measures are needed for prediction.

The power analysis was performed with an estimated 50 subjects per treatment. With a cohort of 50 subjects (on SSRIs), we can detect a true correlation as low as 0.39, with 80% power (two-tailed analysis, Δ = 0.05). In our FDG treatment study, the observed R2 value was 0.32, meaning the true correlation between the data was 0.57 (significantly higher than 0.39). However, this is almost certainly an overestimation because only the voxel cluster highly correlated to the outcome was chosen (as in all cited studies).

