Aim 2: The change in MRgIu from pre to post treatment (SSRI and placebo) will be calculated in the midbrain cluster defined by our preliminary studies. The correlation between this value and Δ HDRS will be assessed with both SSRI and placebo groups as well as with separate cohorts, to determine if there is an effect of treatment. As with Aim 1, a post hoc analysis will also be performed examining this correlation over all voxels.

Power Analysis. The partial correlation for each cluster and the factor related to "loss" varies between 0.5 and 0.6, meaning the true correlation ranges between 0.71 and 0.77. Based on this, using a single cohort (n=50), a true correlation as low as 0.39 can be detected with 80% power (two-tailed analysis, Δ =0.05).

When cohorts are combined (n=100 completers, of 120 enrollees), a correlation as low as 0.27 can be detected.

Aim 3: In a previous cohort, we investigated SimE performance with FDG (and four other tracers). The optimal timing for the blood sample used to anchor the FDG SimE estimation was found to be 40 minutes after injection. At this time, FDG venous and arterial samples are essentially interchangeable. Results using this 40-minute blood-based anchor show that SimE-derived MRGlu are close to MRGlu derived using arterial sampling-based estimation: slope 0.730, correlation 0.955 with compartmental analysis slope 0.876, correlation 0.974 with Patlak analysis. Validation: Validation will be considered complete when MRGlu using conventional (Patlak) analysis and arterial samples matches MRGlu calculated with SimE and one venous sample in the proposed study data. The threshold will be a correlation of at least 0.95 and slope of 0.85 in at least 30 subjects.

F. FUNDING STATUS

This study will be funded through the National Institute of Mental Health (R01MH104512-01A1; 1123782-1-70976), the DANA Foundation (Coeus Proposal #20458, PN15125265; 1128493-1-73073), the Brain and Behavior Research Foundation, (Grant #24459; 1134680-1-75849), internal funding from the Department of Computer Science and pilot funding provided by the Department of Radiology for PET/MRI scan costs.

G. DATA and SAFETY MONITORING PLAN (for more than minimal risk studies)

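### Aim 1 extends its claim of clinical applicability to the post hoc whole-brain search, and counts as differential prediction two patterns that do not test whether the arms differ

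*Combined protocol and SAP*

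**What the plan says.** Section E (Statistics), Aim 1 sets out two analyses. The main one is confined to the regions named in section A: "Correlation between HDRS and pretreatment MRglu will be determined in the ESC and placebo treatment groups in the three specified regions". The second is a search: "In post hoc analysis, spatial resolution will be improved through examination of correlation between whole brain voxel MRglu and HDRS using SPM8".

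One list of outcomes then serves both: "For both analyses, outcome possibilities include: differential treatment Δ HDRS prediction". Three forms of differential prediction follow:

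- significant correlations of opposite sign in the two arms;
- "significant correlation, within different regions, for placebo and ESC";
- a significant correlation in one shared region with the same sign in both arms.

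The only other entry is no significant correlation in either arm. Of everything before that last entry the plan says: "The former outcomes would be immediately clinically significant and applicable".

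The documents give no voxel or cluster threshold, no family-wise or false-discovery control, no arm-by-MRGlu interaction test and no replication step. The power paragraph covers a single correlation in 50 subjects, two-sided at 0.05. That paragraph also says the earlier correlation of 0.57 is probably too high, because "only the voxel cluster highly correlated to the outcome was chosen".

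**The concern.** There are three faults, and a voxel threshold alone would not cure them.

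1. **Scope.** The search is labelled post hoc, but the label does not limit the conclusion. A voxel finding earns the same statement about clinical use as a finding in a pre-specified region.
2. **Inference.** A claim that a marker predicts response to escitalopram differently from response to placebo is a claim about a difference between two correlations. Testing each arm against zero and comparing where significance falls does not test that difference. The same-region, same-sign pattern points, if anything, to prediction that is not specific to treatment.
3. **Selection.** A peak chosen because it is large overstates the true correlation. The plan recognises this in its preliminary data but states no safeguard for its own search.

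The trial's purpose is treatment selection. A marker declared applicable on this basis could be false, inflated, or merely prognostic in both arms.

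**Working it through.** **Inputs from the plan:** 50 per arm; two-sided 0.05; detectable correlation 0.39 at 80% power; three regions; two arms.

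**Assumptions, not in the documents:** 100 to 500 independent elements (M) per voxel map; an uncorrected voxel threshold of 0.001 as an illustration.

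**Step 1. Reproduce the plan's figure.** By Fisher z, power = Φ(atanh(r)·√(n−3) − 1.960). For r = 0.39 and n = 50 this is Φ(0.412 × 6.856 − 1.960) = Φ(0.863) = 0.806. The plan's 0.39 is confirmed.

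**Step 2. Does per-arm significance show a difference?** Suppose r = 0.39 in both arms, so there is no differential prediction. In one region, the chance that exactly one arm is significant is 2 × 0.806 × 0.194 = 0.31. This is the one-region building block of the different-regions pattern, not the probability of the full pattern.

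The opposite-sign pattern is different. Significance at 0.05 needs |r| > 0.279, so two opposite significant results differ by at least 2 × 0.287 = 0.573 on the z scale. The standard error is √(2/47) = 0.206, which gives 2.78, above 1.96. In a pre-specified region that form does imply a difference.

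**Step 3. False peaks in the voxel maps, no true signal.** The chance of at least one false peak in a map is a = 1 − (1 − p)^M. The arms contain different patients, so the chance for both maps is a².

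| Threshold (uncorrected) | M | One map | Both maps |
|---|---|---|---|
| 0.001 | 100 | 0.095 | 0.009 |
| 0.001 | 200 | 0.181 | 0.033 |
| 0.001 | 500 | 0.394 | 0.155 |
| 0.05 | 100 | 0.994 | 0.988 |
| 0.05 | 500 | ~1 | ~1 |

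If each map holds one false peak, they coincide with chance 1/M, that is 1% to 0.2%. Once both maps contain noise peaks, the different-regions pattern is therefore almost always met.

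**Step 4. Does correction within each map suffice?** With family-wise control at 0.05 per map, false peaks in both arms fall to 0.05² = 0.25%, and in at least one arm to 1 − 0.95² = 9.75%. Noise is reduced, but the arms are still not compared.

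**Step 5. Selection.** At p<0.001 and n = 50 the critical |r| is 0.451. Any voxel declared significant must show at least that, whether its true correlation is 0 or 0.39.

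**Step 6. The three-region test.** With independent tests at 0.05 and no signal, a false positive has chance 1 − 0.95³ = 0.143 in one arm and 1 − 0.95⁶ = 0.265 over both. No multiplicity rule is stated here either.

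**Step 7. Power of a direct comparison.** For 0.39 versus 0, power = Φ(0.412/0.206 − 1.960) = Φ(0.036) = 0.51. At 0.05/3 (critical value 2.394) it is Φ(1.996 − 2.394) = 0.35. At 0.05, 80% power needs about 0.52 versus 0, or 0.28 versus −0.28.

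**The case against.** The best defence is that the hypothesis is confined to three named regions, that the search is called post hoc and is meant to sharpen spatial resolution, and that the applicability sentence is conditional. It is not a decision rule and triggers no clinical use. That is fair as to tone, and the three-region correlations themselves are unaffected. It does not remove the words "For both analyses, outcome possibilities include", which tie the search to the list, nor does it make the listed patterns a comparison of arms.

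A reader might infer more than the documents support:

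- **That a false voxel finding is practically certain.** This needs uncorrected 0.05 on the maps. That 0.05 belongs to the power calculation for one correlation. The plan is silent on the voxel threshold; it does not say the maps will be uncorrected.
- **That the risk at 0.001 is 18 to 63%.** That is the chance of a false peak in at least one map (1 − (1 − a)²). The different-regions pattern needs significance in both arms, for which the range is about 1 to 15%.
- **That noise peaks would pass for the effect the trial is powered for.** The largest null |r| averages 0.38 to 0.44 for 100 to 500 elements, close to 0.39. But 0.39 is a detectable effect for one planned test, not a voxel cut-off. The average noise peak falls below 0.451 and would not be significant at 0.001.
- **That Aim 2 has the same fault.** It plans a similar search ("a post hoc analysis will also be performed examining this correlation over all voxels") and also gives no threshold, but attaches no applicability statement.

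**Conclusion.** The concern holds in a limited form. As written, Aim 1 lets a post hoc voxel search support a claim of clinical applicability. It also accepts as differential prediction two patterns that do not show a difference between arms. That logical fault needs no assumption about voxel thresholds and would survive correction within each map. The 31% figure assumes only a true correlation of 0.39 in both arms and 50 per arm.

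The false-peak risk is less certain. It depends on a threshold the plan does not state and on an assumed 100 to 500 independent elements per map. The unstated threshold alone would be a missing detail; the inference attached to the maps is why the text should be changed before analysis.

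**What to change.** 1. **Limit the applicability conclusion** to the three pre-specified regions, and there only when a direct arm-by-MRGlu interaction test on change in HDRS is significant after multiplicity correction over the three regions, for example by Holm's method.
2. **Relabel the outcomes.** Remove the same-region, same-sign pattern from the differential list and call it non-specific prediction. Do not treat significance in different regions as differential without the interaction test.
3. **For the voxel work,** base any claim of differential prediction on one arm-by-MRGlu interaction map with family-wise error control, and state the threshold in advance. Report per-arm maps as descriptive and all hits as hypothesis-generating. Quote no effect size from a selected peak unless it is cross-validated.

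This changes the analysis text and adds one contrast to data already being collected. The cost is fewer claims from the exploratory maps and a less powerful main test: about 0.51 for 0.39 versus 0 at 50 per arm, and about 0.35 at the strictest Holm step. The plan should state that limitation, since a null interaction would then be weak evidence against a differential effect.

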COMMITTEES ON RESEARCH INVOLVING HUMAN SUBJECTS Established 1971

Protocol Summary Form

TITLE: Advancing Personalized Antidepressant Treatment Using PET/MRI **INVESTIGATORS:** [name] Co-Investigators: [name], PhD, [name], [name], [name], [name], [name], [name] [name], [name], PhD, [name], PhD **Department**: Psychiatry

A. SPECIFIC AIMS:

Despite the burden of failed trials, there are currently no tools for treatment selection in Major Depressive Disorder (MDD). Referring to a recent Positron Emission Tomography (PET) study using 2-[¹⁸F]-fluorodeoxyglucose (FDG), NIMH Director [name] remarked that PET imaging is "on the cusp" of aiding in MDD treatment decisions. To finally realize this goal, the limitations of previous FDG studies must be addressed, including limited sample size, lack of placebo comparison (the placebo effect is a significant obstacle to evaluating treatment mechanism and efficacy), and use of relative outcome measures. In the proposed study, FDG imaging before and after Selective Serotonin Reuptake Inhibitor (SSRI) treatment will be performed using a simultaneous PET/Magnetic Resonance (MR) scanner and: (1) the largest sample size to date; (2) a placebo group; and (3) full quantification using analysis of FDG activity in plasma, which yields more accurate estimates of metabolism than relative activity.

Aim 1: Determine a Pretreatment Marker of SSRI Effectiveness Using PET. With the goal of reducing MDD burden, many studies have assessed the utility of FDG-PET in antidepressant treatment prediction. However, due to the limitations listed above, there is no consensus on which brain regions are predictive of treatment efficacy. In addition to serving as a biomarker of SSRI effectiveness, only conclusive determination of these regions will provide insight into depression pathophysiology, helping uncover SSRI mechanism of action, and aiding in the search of novel therapeutics. Based on our preliminary data and other, similar studies, we hypothesize that SSRI-induced change in the Hamilton Depression Rating Scale (Δ HDRS) will be correlated with pretreatment metabolic rate of glucose (MRGlu, quantified using arterial blood analysis) in three potential regions: (1) midbrain, (2) right anterior insula, and/or (3) left ventral prefrontal cortex.

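### Aim 1 tests three regions in the SSRI arm with no multiplicity rule; the detectable correlation of 0.39 at n = 50 applies to one region tested alone (about 0.44 per region with Bonferroni)

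*Combined protocol and SAP*

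**What the plan says.** In the combined protocol and SAP, section A (Specific Aims, Aim 1) hypothesises that HDRS change under SSRI correlates with pretreatment MRGlu in "three potential regions: (1) midbrain, (2) right anterior insula, and/or (3) left ventral prefrontal cortex". As motivation it says that "there is no consensus on which brain regions are predictive of treatment efficacy" and that "only conclusive determination of these regions will provide insight into depression pathophysiology".

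Section E (Statistics, Aim 1) says the correlation "will be determined in the ESC and placebo treatment groups in the three specified regions". A whole-brain voxel analysis follows and is labelled post hoc.

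On sample size: "The power analysis was performed with an estimated 50 subjects per treatment", and for the 50 patients on SSRI, "we can detect a true correlation as low as 0.39, with 80% power". The level is given as two-tailed 0.05. It is printed with a delta sign, read here as alpha.

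The document names no primary region, no order of testing, no significance threshold for the analysis itself and no adjustment for testing three regions.

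**The concern.** The *and/or* in the hypothesis makes Aim 1 a claim over three tests, because a significant result in any one region counts as support. The only error level in the text is 0.05, in the power sentence. If each region is tested at that level, the chance of declaring at least one region predictive when none is exceeds 5%.

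The stated power has the matching gap. It describes one test at the full 0.05, while the aim runs three, and the text does not say which is meant.

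This matters because the conclusions are to be drawn by region. The aim is to settle which regions are predictive where earlier studies disagree, and section E lists outcomes that differ by region and regards them as directly usable in the clinic. Section E also concedes that its preliminary correlation of 0.57 is inflated because the best-correlated voxel cluster was picked. Picking the best of three regions without adjustment is a milder form of the same selection.

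**Working it through.** **Inputs from the document.** Three regions (section A, Aim 1). 50 SSRI patients, two-sided 0.05, 80% power, detectable correlation 0.39, preliminary R² of 0.32, i.e. r = 0.57 (section E, Aim 1). For the combined cohorts, n = 100 and 0.27 (section E, Aim 2).

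**Assumed.** The correlation between regional MRGlu values is not given, so a range is shown.

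**1. The plan's own figure.** By Fisher z, detectable r = tanh((z₁₋α/₂ + z₀.₈₀)/√(n − 3)).
- α = 0.05, n = 50: tanh((1.960 + 0.842)/√47) = tanh(0.409) = 0.387. The plan's 0.39 is reproduced as a single unadjusted test.
- Power at r = 0.39: atanh(0.39) × √47 = 2.823, and Φ(2.823 − 1.960) = 0.806.

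**2. Family-wise error, three SSRI-arm tests each at 0.05.** If the regions are independent, 1 − 0.95³ = 0.143. Simulation (200,000 trials, n = 50, t-test of r) gives:

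| Assumed inter-region correlation | 0 | 0.3 | 0.5 | 0.8 | 0.9 | 0.95 |
|---|---|---|---|---|---|---|
| Chance of at least one false positive | 14.2% | 13.6% | 12.6% | 9.9% | 8.5% | 7.5% |

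**3. Per-region figures with Bonferroni (α = 0.05/3 = 0.0167, z = 2.394).**
- Detectable r at n = 50: tanh((2.394 + 0.842)/√47) = tanh(0.472) = 0.440.
- n needed for r = 0.39 at 80% power: ((2.394 + 0.842)/0.4118)² + 3 = 64.7, so 65. The same formula at α = 0.05 gives 49.3, so 50.

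| True correlation | Power, one test at 0.05 | Power per region at 0.05/3 |
|---|---|---|
| 0.39 | 80.6% | 66.6% |
| 0.50 | 96.5% | 91.5% |
| 0.57 | 99.3% | 98.0% |

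**4. Less conservative adjustments.** A max-statistic test uses the correlation between regions. Its critical p is 0.0174, 0.0184, 0.0237, 0.0280 and 0.0321 at assumed correlations of 0, 0.5, 0.8, 0.9 and 0.95. The detectable r is then 0.438, 0.435, 0.424, 0.416 and 0.410. With Holm, simulated power per real region at r = 0.39 is 67–68% if one region is real, 70–71% if two are and 73–77% if all three are.

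**5. Chance of detecting at least one real region** (simulated, r = 0.39, Bonferroni): 67% if one region is real; 77–90% if two are (assumed correlation 0.8 down to 0); 77–97% if three are (0.9 down to 0). With one or two real regions at 0.39 and the rest at zero, an inter-region correlation of 0.9 is mathematically impossible, so the two-region range stops at 0.8.

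**6. Side check, Aim 2.** At n = 100, tanh(2.802/√97) = 0.277. Power is 77.8% at 0.27 and 80.9% at 0.28.

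**The case against.** The strongest reply has four parts.

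- **The 0.39 is not an arithmetic error.** The plan gives n, sidedness, level and power, so a statistician can recognise it as a single-test figure. This stands, but the text never links that figure to a three-region claim.
- **Per-region power is the wrong yardstick for an *and/or* hypothesis.** The relevant power is then the chance of finding at least one real region, which reaches or exceeds 80% at 0.39 in many scenarios with two or three real regions. This stands in part. If only one region is real, it is 67%. And if the aim is to say which regions are predictive, power per region is what counts.
- **The 14% is an upper bound.** Absolute regional MRGlu values may well be positively correlated, and the three regions are few and prespecified. This is fair, but the error stays above 5% at every correlation examined. Prespecification limits the family to three; it does not set the error rate over the three.
- **The choice of family is open.** The plan also tests the placebo arm. Counting six tests would give a detectable correlation of 0.468 with Bonferroni, and an unadjusted family-wise error of 26.5% under independence. The three SSRI tests are used here because the stated hypothesis concerns SSRI-induced change. This is the milder case.

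**Conclusion.** The concern holds. As written, the plan leaves error control for Aim 1 undefined. Testing each region at the only level stated gives a family-wise error in the SSRI arm of roughly 7.5% to 14%, depending on an inter-region correlation that the document does not give.

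The 0.39 is right for one test. The corresponding per-region figure is 0.44 with Bonferroni, or 0.41 to 0.44 with a max-statistic test.

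The consequence is moderate. The design remains usable, and power is high if the true correlation is 0.50 or more. The preliminary 0.57 cannot be relied on to place the truth there, since the plan itself calls it an overestimate. The power figures rest on the Fisher z approximation and 50 SSRI completers.

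**What to change.** 1. **State the multiplicity rule.** Prespecify Holm, or a max-statistic permutation test, over the three SSRI-arm regions at a two-sided family-wise level of 0.05.
2. **Restate the power sentence**, for example: *With 50 ESC completers, the detectable correlation at 80% power is 0.39 for a single test and about 0.44 per region after adjustment for three regions (two-sided alpha 0.05).*
3. **Minor, Aim 2.** Where section E says "a correlation as low as 0.27 can be detected" for the combined cohorts, the figure should be 0.28.

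The cost is two sentences and a less favourable stated figure. No patients are added if about 0.44 per region is accepted. Keeping 0.39 per region at 80% power with Bonferroni would need about 65 SSRI completers, 15 more than planned.

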Aim 2: Isolate the Neurobiological Basis of the "Loss" Research Domain Criteria (RDoc) and the Change Associated with Treatment. Using a factor analysis of the HDRS, we have previously demonstrated that the "loss" RDoC criteria is significantly correlated to MRGlu in frontal cortical areas. We therefore hypothesize that change in MRGlu (pre to post treatment) in these regions will be correlated with symptom improvement specifically in "loss" symptoms. As an exploratory extension, we will determine whether these changes are treatment-specific (i.e. to SSRI or placebo). A validation of our hypothesis suggests a targeted mechanism of action, and provides

a significant step forward for precision treatment. If regional changes in MRGlu are not correlated to improvement in this RDoC category, it suggests that SSRI (or placebo) induced changes may be a downstream effect that should be examined further.

Aim 3: Validate NonInvasive Full Quantification of MRGlu Using Simultaneous Estimation. Full quantification of brain MRGlu with FDG (as performed in this study) requires measuring FDG in arterial plasma (input function) from arterial catheter insertion and blood analysis. This costly and invasive procedure creates a barrier to widespread PET use. Our group has developed an innovative method for Simultaneous Estimation (SimE) of input information and PET outcome measures (e.g., MRGlu). SimE fully quantifies brain MRGlu without requiring an arterial catheter. In the case of FDG, our data suggests that SimE used with a single venous sample can provide accurate results. We further hypothesize that the venous sample may be entirely replaced by study data (e.g., injected dose) and biometrics (e.g., body surface area, lean body mass index). Using two different approaches (statistical imputation and physiological parametric modeling) and previously collected data, we will train the SimE for accurate quantification in the absence of blood data. The rich data collected in this study will then provide a robust benchmark for validation of the SimE approach.

B. BACKGROUND AND SIGNIFICANCE:

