Despite current medications, morbidity and mortality of Major Depressive Disorder (MDD) remain high. (Benton, Staab et al. 2007) According to the World Health Organization, MDD affects 121 million people worldwide, and is projected to be the second leading cause of global disability by 2020. Monotherapy with SSRIs is the most widely used treatment for MDD. (Leuchter, Lesser et al. 2008) However, on average, SSRIs require six weeks for onset of action, and two-thirds of those on SSRIs fail to achieve remission.(Trivedi, Rush et al. 2006, Leuchter, Cook et al. 2010) Compounding this problem, patients with residual symptoms are significantly more likely to discontinue treatment or relapse, be hospitalized for medical and psychiatric conditions, or die of suicide and other causes.(Trivedi 2003, Trivedi, Rush et al. 2006, Warden, Trivedi et al. 2007) Although eliminating ineffective treatment trials would significantly reduce patient suffering and healthcare costs, (Taylor, Youngblood et al. 2005, Leuchter, Cook et al. 2010) clinicians currently do not have the tools to objectively select treatment based on an individual's likelihood of remission. Therefore, there is an urgent need to identify markers predictive of an individual's SSRI treatment outcome (Taylor, Youngblood et al. 2005, Leuchter, Cook et al. 2010). Developing this personalized treatment requires increased understanding of the relationship between pretreatment neurobiology, SSRI-induced biological changes, and the corresponding symptom improvements.

Our proposed study, in which FDG-PET scans are acquired before and after escitalopram (or placebo) treatment, avoids these previous limitations by standardizing treatment across all subjects, enrolling 120 subjects to ensure that at least 100 will complete the protocol (largest sample size to date), performing full quantification with arterial blood sampling, and a priori defining the clinical outcome measure as Δ HRDS. Further, we will uncover neurobiological correlates of pathophysiology that span diagnoses.

Potential Noninvasive Estimation: PET research/clinical laboratories have differing levels of software and/or hardware expertise. The key, therefore, to promoting widespread PET use is to develop multiple, validated pathways for noninvasive imaging. In this study, we will evaluate Simultaneous Estimation.

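### The Aim 2 analysis sentence (midbrain MRGlu change against Δ HDRS) does not test the Aim 2 hypothesis (frontal MRGlu change against loss symptoms), and it does not match its own power paragraph

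*Combined protocol and SAP*

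**What the plan says.** Four places bear on Aim 2.

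- **Hypothesis (section A, Aim 2).** Earlier work is said to show that the loss RDoC "criteria is significantly correlated to MRGlu in frontal cortical areas". From this the plan hypothesises that "change in MRGlu (pre to post treatment) in these regions will be correlated with symptom improvement specifically in" loss symptoms. Confirmation is to be read as evidence of a targeted mechanism. A null result is defined by the same outcome: "If regional changes in MRGlu are not correlated to improvement in this RDoC category", the change is to be read as possibly downstream.
- **Analysis (section E, Aim 2).** MRGlu change "will be calculated in the midbrain cluster defined by our preliminary studies", and its correlation with Δ HDRS is assessed in the two treatment groups together and separately. Section A, Aim 1, introduces Δ HDRS as "SSRI-induced change in the Hamilton Depression Rating Scale", with no restriction to a factor. After the main analysis, "a post hoc analysis will also be performed examining this correlation over all voxels".
- **Power (section E, Aim 2, next paragraph).** "The partial correlation for each cluster and the factor related to" loss is put at 0.5 to 0.6, and detectable correlations of 0.39 (n=50) and 0.27 (n=100) are given.
- **Study-wide outcome (section B).** The study is described as "a priori defining the clinical outcome measure as" the change in the Hamilton scale.

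**The concern.** The only sentence that says how Aim 2 will be analysed differs from the hypothesis in both region and outcome. Midbrain is a hypothesised region under Aim 1, not Aim 2. Both announced interpretations depend on the loss outcome, so a result for midbrain change against Δ HDRS could not properly be given either one.

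The word *specifically* makes the outcome mismatch the more serious of the two. A correlation with the whole scale, in any region, cannot separate loss symptoms from the rest. If the texts stay as they are, region and outcome could also be chosen after the data are seen and the result still reported as Aim 2.

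**Working it through.** **1. The texts side by side**

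| Text | Region | Brain measure | Clinical outcome |
|---|---|---|---|
| Section A, Aim 2 hypothesis | frontal cortical areas | MRGlu change | improvement in loss symptoms |
| Section E, Aim 2 analysis | one midbrain cluster | MRGlu change | Δ HDRS |
| Section E, Aim 2 post hoc | all voxels | MRGlu change | Δ HDRS (same correlation) |
| Section E, Aim 2 power | clusters, plural; region not named | not stated to be change | loss factor |

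The analysis conflicts with the hypothesis on region and outcome. It conflicts with the power paragraph on outcome and on one cluster versus several. The post hoc analysis repairs the region but not the outcome. Section E does not use the word total, but whole-scale change is the plain reading of the section A definition.

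**2. The plan's own figures**

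Inputs from section E: two-sided 0.05, 80% power, n=50 and n=100. By Fisher z, the smallest detectable correlation is r = tanh[(1.960 + 0.842)/√(n−3)].

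- n=50: tanh(2.802/6.856) = 0.387, stated as 0.39.
- n=100: tanh(2.802/9.849) = 0.277, stated as 0.27. Power at exactly 0.27 is 77.8% by this method; other two-sided methods give 78.2% to 79.3%.

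The figures reproduce to within about two points of power. The formula contains no region and no outcome, so realigning the analysis leaves them unchanged for a single test at 0.05. What does not carry over is the expected effect. The 0.5 to 0.6, and the 0.71 to 0.77 that the plan derives by taking square roots, belong to the loss factor. The documents give no figure for midbrain change against Δ HDRS.

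**3. Would switching to a loss score be enough?**

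This is an illustration on assumed inputs. Suppose MRGlu change relates to symptoms only through non-loss items, with r = 0.387 at n=50. The correlation with another score is then r × q, where q is that score's correlation with non-loss change. The chance of significance at two-sided 0.05 follows from Fisher z.

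- Δ HDRS, q assumed 0.8 to 0.95: r × q = 0.310 to 0.368, significant in 59% to 75% of studies.
- Loss score, q assumed 0.3 to 0.7: r × q = 0.116 to 0.271, significant in about 13% to 48% of studies.

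The loss score is less misleading than Δ HDRS, but a significant loss correlation alone does not show specificity either. That needs a direct comparison of the loss and non-loss correlations. If instead the effect runs only through loss, simulation of a test of dependent correlations (Meng's z) gives power of about 19% to 38% at r = 0.387 (n=50), for loss/non-loss correlations of 0.7 down to 0.3. The range is the same at r = 0.277 (n=100). At r = 0.5 power is 32% to 62% (n=50) and 59% to 90% (n=100).

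**4. Multiplicity once clusters are named**

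The documents do not give the number of frontal clusters, so no adjusted figure can be fixed. As an illustration, three clusters with Bonferroni (alpha 0.05/3, z = 2.394) give tanh[(2.394 + 0.842)/6.856] = 0.44 at n=50 and tanh[(2.394 + 0.842)/9.849] = 0.32 at n=100.

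**The case against.** The best defence is that the analysis sentence may be deliberate: section B makes change in the Hamilton scale the a priori clinical outcome for the study. Alternatively it may be a drafting slip in a summary form, with masks and factor scoring already fixed in the earlier work that the plan mentions. Both are possible. Neither resolves the conflict. If the sentence is deliberate, the hypothesis and power paragraph are wrong for it. If it is a slip, the aim's only analysis sentence still omits the loss test, and section E cites no frontal masks or loss scoring for Aim 2.

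Four stronger readings are tempting, and the documents do not support them.

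- *That the power paragraph also specifies frontal change.* It names neither frontal regions nor change. The frontal link comes from section A.
- *That section E ignores loss altogether.* Its power paragraph is built on the loss factor. Section E contradicts itself; it is not silent.
- *That the sample size or detectable correlations are wrong because of the mismatch.* They do not depend on it.
- *That a definite amount of power is lost by using Δ HDRS.* Any such figure needs a loss/total correlation, which the documents do not give. It would also have to fit the other assumptions: if loss and non-loss change correlate at 0.7, loss and their total cannot correlate below 0.7.

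It is also fair to object that a loss-score correlation does not by itself establish specificity. That stands, and the remedy has to say so.

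**Conclusion.** The conflict is on the page and no other text resolves it. One of three aims has an analysis sentence that does not test its stated hypothesis and supports neither announced interpretation. This conclusion rests on the quoted texts, and on reading Δ HDRS as change in the whole scale; it needs none of the assumed correlations.

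The size is one of validity. The documents do not allow a numerical loss to be stated, and the stated 0.39 and 0.27 stand. Confidence is high for the inconsistency. The percentages in steps 3 and 4 of the working are illustrations that rest on assumed correlations and an assumed cluster count. It should be corrected before analysis, because a text change is enough to remove the problem.

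**What to change.** Reconcile the Aim 2 texts in writing before analysis, by one of two routes.

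**Option A (fits the section A hypothesis and the loss-factor power text).**
- Make the Aim 2 analysis the correlation between change in the HDRS loss-factor score, baseline to second scan, and MRGlu change in the frontal clusters from the preliminary loss-factor work.
- Cite the existing masks and item scoring, state the number of clusters, and adjust for multiplicity across them.
- Keep midbrain change against Δ HDRS as secondary and the all-voxel analysis as exploratory.
- State that a loss-score correlation alone does not show specificity. Report the loss versus non-loss difference in correlations with a confidence interval, claim specificity only if that comparison supports it, and disclose its low power near the detection limit.
- Restate the power paragraph at the adjusted alpha once the cluster count is given.

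**Option B (if midbrain against Δ HDRS was intended).** Restate the Aim 2 hypothesis, its interpretations and the power paragraph to match, and drop the claim about loss symptoms.

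**Cost.** Section D already plans HDRS after washout and at visits, and both scans, so neither option adds a visit or procedure. Option A requires HDRS to be kept at item level, raises the detectable correlation somewhat, and may leave the specificity comparison inconclusive. Option B needs only rewording but gives up the loss-specific aim.
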